Subjects will be paid \$100 total per set of evaluations. For pre- and post-testing, the participant will receive \$25 for each type of evaluation completed (i.e., clinical hand function, MRI, TMS, and EEG) for a total of \$100. For follow-up evaluations, the participant will receive \$33 for clinical hand function, \$33 for TMS, and \$34 EEG for a total of \$100. The participant will receive \$25 per therapy visit for participation in this study. There will be a total of 11 evaluations sessions and 6 therapy visits. If they complete all evaluations and therapy visits, they will receive a total of \$450. If they stop participating in the study, they can keep the payment they have already received, but will not receive any more compensation. If the subject does not complete one of the assessments due to scheduling conflicts or safety risks (see Section 2.b.), the subject will not receive remuneration for that portion of the study. The payment will be in cash, at the end of each visit.

Analysis: Repeated measures ANOVA with post hoc comparisons will be used to determine if each clinical hand function score improves more for the experimental compared with the control group. A significant interaction between time (pre, post, 2 weeks after) and group (experimental/control) will support the hypothesis. Pearson's correlations between the mean change in clinical hand function scores and each of the neurophysiologic measures will be examined to identify relevant neurophysiologic measures for hand function.

Expected Outcomes: Greater recovery of dexterous hand function is expected with the light vibration stimulation (with a significant session×group interaction). This exciting finding will be the first to demonstrate that this unperceivable vibration stimulation at the wrist improves hand therapy outcomes.

E. PROTECTION OF HUMAN SUBJECTS

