1. Loss of confidentiality: Appropriate steps will be taken to protect any information collected. The data from test results will be de-identified once it has been collected and before it is stored. This means individual results would not be able to be linked to the subject by others who review the results of this research. The linkage between subject codes and identities as well as all other identifiable information including consent/HIPPA forms will be stored in a locked room and be accessible only to the study personnel.

2. TMS: The MUSC Brain Stim Laboratory requires that all subjects receiving TMS and MRI complete a screening questionnaire to ensure that the person does not have any loose metal objects like earrings or nose rings or a piece of metal in the body such as a fragment in the eye, aneurysm clips, ear implants, spinal nerve stimulators, a pacemaker, or an implant electrical device. A person must be screened before each TMS and/or MRI exam. Persons who do not meet the screening criteria for TMS or MRI may still be considered eligible for the study, but will not complete these evaluations.

The primary safety concern with TMS is the induction of seizures; however, the incidence of seizures is very low and mostly associated with high frequency repetitive TMS (rTMS) which will not be used in this project. Instead we will use single-pulse TMS, which is much safer and we will follow published "gold standard" safety guidelines for diagnostic TMS to minimize the risk of inducing a seizure (*Groppa et al. 2012*).

Hearing protection for all subjects during TMS will be provided. Stimulation sessions will be stopped immediately with any complaints of discomfort or for any complaints of dizziness or light-headedness. There are no lower-risk methods available to gain the same scientific information.

A TMS stimulus may feel like a slight tap on the skull. There is a very low risk of scalp discomfort. The subject will be asked to notify the experimenter if s/he experiences these. The headache or changes in cognitive function is expressed, the subject will stop participating in the study.

Persons with potential for pregnancy will not have the TMS stimulation. Persons with a history of seizures will not have the TMS stimulation.

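### Assessments not completed for safety reasons go unpaid, which gives subjects a modest financial incentive not to disclose TMS or MRI risks

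*Combined protocol and SAP*

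**What the plan says.** Section D (Research Design and Methods) sets the payments. Each of the four evaluation types earns $25 at pre-testing and again at post-testing, so each of these sets is worth $100. The follow-up set, which has no MRI, is also worth $100: clinical hand function and TMS earn $33 apiece, and EEG earns $34. A therapy session earns $25. The paragraph gives this count: "There will be a total of 11 evaluations sessions and 6 therapy visits". The stated total is $450, in cash at the end of each visit.

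Two rules in the same paragraph say what goes unpaid. When an assessment is not completed because of scheduling conflicts or "safety risks (see Section 2.b.), the subject will not receive remuneration for that portion of the study". On leaving the study: "If they stop participating in the study, they can keep the payment they have already received, but will not receive any more compensation".

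Section E.2.b (Protection against Risk) describes how risks come to light. The subject completes a screening questionnaire and is screened before each TMS or MRI exam. A TMS session is stopped when the subject complains of discomfort, dizziness or light-headedness. On scalp sensations and discomfort: "The subject will be asked to notify the experimenter if s/he experiences these". The sentence after it deals with two further symptoms and reads: "The headache or changes in cognitive function is expressed, the subject will stop participating in the study".

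Sections E.1.a, E.2.b and E.5 also say that a person with a TMS or MRI contraindication may still be considered for the study and omits only those evaluations.

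**The concern.** The payment rule and the safety rules pull in opposite directions. Safety depends largely on what the subject says, and the subject is paid less for saying it. The payment rule cites the safety section by number, so the link does not depend on a strained reading.

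Two things are at stake. The first is protection against the risks that section E.1.c names, among them seizure with TMS and movement of iron-containing objects. The second is the adverse-event record. Section E.5 says that all adverse events will be documented and reported to the IRB, yet a headache, a TMS risk named in section E.1.c, could cost a subject most of the payment to mention. The point does not touch the sample size, the error rates or the comparison of hand function between groups.

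**Working it through.** **1. Reproduce the plan's total (section D).**

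- Pre-testing: 4 × $25 = $100
- Post-testing: 4 × $25 = $100
- Follow-up: $33 + $33 + $34 = $100
- Therapy: 6 × $25 = $150
- Total: $100 + $100 + $100 + $150 = $450. Evaluations: 4 + 4 + 3 = 11. Both match the protocol.

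**2. Pay lost by declaring a contraindication.** MRI is not part of follow-up, so it is paid at two time points and TMS at three.

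| Declared bar | Sum | Share of $450 |
|---|---|---|
| TMS | $25 + $25 + $33 = $83 | 18% |
| MRI | $25 + $25 = $50 | 11% |
| Both | $83 + $50 = $133 | 30% |

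**3. Pay lost by expressing a headache or cognitive change at TMS.** Here the stop-participation sentence in section E.2.b combines with the no-further-compensation rule in section D. I assume that evaluations run in the order in which section E.1.a numbers them: clinical, MRI, TMS, EEG. That section supports MRI before TMS, because the anatomical scan is used to locate the TMS target. The protocol does not say whether a session stopped midway counts as completed, so each result is a range.

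| Where it happens | Already earned | Lost if that TMS is unpaid | Lost if that TMS is paid |
|---|---|---|---|
| Baseline | $25 + $25 = $50 | $450 − $50 = $400 (89%) | $375 (83%) |
| Post-therapy | $100 + $150 + $50 = $300 | $150 (33%) | $125 (28%) |
| Follow-up | $100 + $150 + $100 + $33 = $383 | $67 (15%) | $34 (8%) |

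**4. Split the baseline figure.** Pay for later visits is $150 + $100 + $100 = $350. Pay still open in the baseline set is $25 to $50. Most of the loss is therefore for visits that would not take place. A different order of evaluations would change only the part inside the $100 baseline set.

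**5. Set detection beside payment.** The contraindication questionnaire and the TMS stopping triggers in section E.2.b start from the subject's own statement. The documents describe no record review, metal detection or pregnancy test that would check the answers. Section D attaches non-payment to the result.

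**6. Cost of paying.** No contraindication rate is given, so I assume 10% to 40% of the 30 subjects are barred from both MRI and TMS and are paid in full for both.

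- 10%: 3 × $133 = $399
- 20%: 6 × $133 = $798
- 40%: 12 × $133 = $1,596
- Planned outlay: 30 × $450 = $13,500

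**The case against.** The strongest reply is that this is ordinary payment per completed task. Subjects keep what they have been paid and go unpaid only for time not given: about an hour for each MRI and half an hour for each TMS. A contraindicated person stays in the study with therapy and the other evaluations paid, which removes the larger motive to conceal. This stands, and it is why the incentive for contraindications is modest.

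A reader might infer that the TMS and MRI safeguards rest on self-report alone, apart from hearing protection. The documents do not support that. Section E.2.b also specifies single-pulse instead of repetitive TMS and published safety guidelines, and section E.5 has the laboratory perform and record screening before each test. The laboratory's own procedures are not in the documents. These measures lower the risk for whoever is stimulated. As described, they do not reveal a contraindication or symptom that the subject keeps back.

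A reader might also infer that any side effect costs the subject money to report. Only headache and cognitive change end participation. Discomfort or dizziness stops the session, and pay for a stopped session is undefined. Skin irritation and hearing loss carry no stated payment consequence.

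Finally, payment is a matter for the IRB, and the consent pages are not available, so what subjects are told cannot be judged. That limits how strongly the point can be put. It does not remove the conflict between sections D and E.2.b.

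**Conclusion.** The point holds as an incentive created by the payment wording. Disclosing a contraindication costs $50 to $133 of $450. Expressing a headache or cognitive change costs $375 to $400 at baseline TMS, $125 to $150 at post-therapy TMS and $34 to $67 at follow-up TMS.

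The headache figures rest on three assumptions: the listed order of evaluations, a literal reading of a sentence that is grammatically incomplete, and either reading of whether a stopped session is paid. It would be wrong to read the 83% to 89% as cash lost at that visit, since $350 is for later visits not attended.

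It is also tempting to conclude that the adverse-event record is biased downwards. The documents show no under-reporting. They show only a reason why it could occur. This is a cheap improvement to subject safety and does not put the trial's analysis in doubt.

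**What to change.** In the payment paragraph of section D, and in the consent discussion before the screening questionnaire is completed, separate safety from scheduling:

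- A TMS or MRI assessment that the subject attended, and that staff withhold or stop for a section E.2.b safety reason, is paid as if completed. This also settles pay for a session stopped midway.
- A subject withdrawn because of a safety symptom is paid for the rest of that evaluation set.
- Missed or declined assessments stay unpaid.

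The investigator should also reconcile the stop-participation sentence in section E.2.b with the no-further-compensation rule in section D. Which clinical rule applies is for the investigator and the IRB.

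The payment change is partial. After a headache at baseline TMS the subject would receive $100, and the $350 for later visits would remain unpaid. At post-therapy TMS, $100 would remain unpaid; at follow-up, nothing. A person barred at initial screening and never booked for MRI or TMS would still go without that pay.

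The cost is a few sentences and at most $133 per barred subject: about $400 to $1,600 under the assumed 10% to 40%, within the planned $13,500, and less if barred subjects are not booked. There are two small downsides: some payments yield no data, and there is a slight reverse incentive to declare a symptom.

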**Medical University of South Carolina
Protocol**

PI Name: [name]

Study Title: Sensory Stimulation to Enhance Hand Function Post Stroke

NCT02675764

TABLE OF CONTENTS

A. SPECIFIC AIMS	2
B. BACKGROUND AND SIGNIFICANCE	2
C. PRELIMINARY STUDIES	2
D. RESEARCH DESIGN AND METHODS	2
E. PROTECTION OF HUMAN SUBJECTS	3
F. REFERENCES/LITERATURE CITATIONS	7
G. FACILITES AVAILABLE	8

A. SPECIFIC AIMS

The objective of this pilot project is to assess the impact of the novel sensory vibration stimulation technique we have developed in enhancing outcomes of hand therapy as well as the central nervous system responsiveness in chronic stroke survivors. This impact will be assessed in a double-blind stratified randomized controlled trial for stroke survivors. The hypothesis is that improvement in hand function will be greater for the experimental group receiving the wrist subthreshold vibrotactile stimulation during therapy compared with the control group who will wear the device with no vibration (placebo), and that this better improvement in hand function is associated with neurophysiologic measures of central nervous system responsiveness.

B. BACKGROUND AND SIGNIFICANCE

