D. RESEARCH DESIGN AND METHODS

The hypotheses will be tested in a double-blind stratified randomized controlled trial. Experimental and control groups will be compared for post-therapy changes in hand function. To obtain two comparable groups, stroke subjects will be stratified by their initial hand motor and sensory scores (Fugl-Meyer and Semmes-Weinstein mild vs. moderate). Subjects will be randomly and blindly assigned to either the experimental or the control group. A standardized task-practice therapy focused on dexterous object manipulation and multi-joint upper extremity coordination will be used, since the intervention targets sensory feedback-based motor control. The research therapists at the SC Stroke Recovery Research Center have been trained in its implementation and routinely use this protocol. Each subject will receive therapy two hours/day, 3 days/week for 2 weeks. The duration of 2 weeks is deemed sufficient to result in statistically greater improvement in motor outcome and cortical reorganization (seen using fMRI/TMS) for the experimental compared to the control group. The two groups will receive therapy of equal intensity individually in the same room supervised by the same therapist who is blinded to the group and does not know how the coin-sized device providing the light vibration works. Tactor (EAI, Casselberry, FL) generating light vibration in our preliminary studies will be applied to the wrist. At the beginning of each therapy session, the subject's sensory threshold will be determined and the vibrating intensity will be adjusted to either 60% of the sensory threshold or zero, depending on the group. Blinding to the light vibration stimulation is possible because subjects cannot perceive subthreshold (imperceptible) vibration, thus they do not know whether they are receiving the vibration or not.

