Evaluation will be performed before (pre-intervention testing), after (post-intervention testing), and 2 weeks after the therapy (follow up testing). Clinical sensorimotor function of the hand will be assessed using clinical tests, such as the Nine Hole Peg, Action Research Arm, Box and Block test to assess dexterity, as well as the Semmes-Weinstein and Grating Orientation tests to assess sensation. Secondarily, the Stroke Impact Scale and Stroke-Specific Quality of Life Scale will be recorded to assess the potential for the light vibration stimulation to impact patients' self-care abilities. Neurophysiologic evaluation will be performed using the MRI including an anatomical scan, diffusional kurtosis imaging (DKI), and functional MRI (fMRI) during grip, TMS including resting and active motor thresholds and motor evoked potential peak-to-peak amplitudes (all of these variables are routinely used in MUSC TMS evaluation protocols), and EEG evoked potentials and frequency power modulation during grip.

Each subject will visit MUSC for a total of 9 to 12 times over a period of a month. The pre-intervention testing will include screening, clinical hand function assessment, MRI, TMS and EEG. There will be six therapy visits lasting 2 hours each. Post-treatment evaluation will include clinical hand function assessment, MRI, TMS, and EEG after the completion of therapy. Follow up testing will include clinical hand function, TMS, and EEG again 2 weeks after the completion of therapy. Each set of evaluations (pre, post, and follow up testing) can be performed over 2 days to minimize participant fatigue.

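### No primary hand test and no rule for how many of the five named tests must succeed: if any one suffices, a false claim of benefit is about 2 to 5 times as likely as with one test

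*Combined protocol and SAP*

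**What the plan says.** Section A (Specific Aims) states a single directional hypothesis, that "improvement in hand function will be greater for the experimental group receiving the wrist subthreshold vibrotactile stimulation", and names no test. Section D repeats the comparison in general terms: "Experimental and control groups will be compared for post-therapy changes in hand function".

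Section D then measures clinical hand function "using clinical tests, such as the Nine Hole Peg, Action Research Arm, Box and Block test to assess dexterity". Two further tests cover the sensory side: "as well as the Semmes-Weinstein and Grating Orientation tests to assess sensation". That makes five named tests, in a list worded so that others could be added. Only the two self-report scales are ranked lower: "Secondarily, the Stroke Impact Scale and Stroke-Specific Quality of Life Scale will be recorded".

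The Analysis paragraph applies repeated measures ANOVA to every score separately; "post hoc comparisons will be used to determine if each clinical hand function score improves more for the experimental compared with the control group". The decision rule follows: "A significant interaction between time (pre, post, 2 weeks after) and group (experimental/control) will support the hypothesis".

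Two other places bear on which tests count. Section E, 1.a, item 5 includes finger sensation in the clinical hand function evaluation, so all five tests qualify. The Expected Outcomes paragraph of section D speaks only of dexterity, which covers three.

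The public text gives no primary hand test, alpha level for this trial, success rule across tests or multiplicity adjustment.

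**The concern.** One hypothesis is tested on at least five scores, and the support rule does not say on which score, or on how many, the interaction must be significant. Suppose the Nine Hole Peg interaction is significant and the Action Research Arm interaction is not. The plan as written allows this to be called support or no support, and the choice would be made with the results in view.

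The rule is stated for an interaction, in the singular, so it invites the reading that one significant score is enough. The text does not settle this. On that reading the chance of a false claim grows with the number of tests.

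Direction is a second gap. The hypothesis is directional, but a three-visit interaction F test is not. The plan does not say whether benefit is judged at post-intervention, at follow-up, at both, or on their average.

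**Working it through.** **No figure to reproduce.** The documents give no error rate, alpha or power. The design figures they do give are 15 per arm (section E, 1.a), three visits and five named tests, three for dexterity and two for sensation (section D).

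**Assumptions not in the plan.** Alpha is 0.05 per test; section C reports earlier results against that level. Any one test suffices. The tests are equally correlated, from 0 to 0.9. There is no true effect.

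**Closed form, independent tests.** P(at least one significant) = 1 − (1 − a)^k.

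- Either direction, a = 0.05: 1 − 0.95^5 = 22.6%, and 1 − 0.95^3 = 14.3%, against 5%.
- Favourable direction only, a = 0.025: 1 − 0.975^5 = 11.9%, and 1 − 0.975^3 = 7.3%, against 2.5%.

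**Simulation of the planned test.** Normal data, 15 per arm, three visits with correlation 0.7; interaction F on 2 and 56 df at 0.05; 40,000 runs per setting (20,000 for the first row). The plan gives no direction rule, so three were tried, each on top of a significant interaction:

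- A: change from baseline, averaged over post and follow-up, favours vibration.
- B: a two-sample t test on change from baseline (28 df, two-sided 0.05) is significant in favour of vibration at post or at follow-up.
- C: as B, at post only.

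False claims (%), any one test sufficing; the correlation between tests is given in the column heads:

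| Rule | One test | Five, 0 | Five, 0.5 | Five, 0.7 | Five, 0.9 | Three, 0 | Three, 0.9 |
|---|---|---|---|---|---|---|---|
| Undirected, as the plan is worded | 5.0 | 22.7 | 18.3 | 14.8 | 10.6 | 14.4 | 8.7 |
| A | 2.5 | 12.2 | 9.7 | 8.0 | 5.4 | 7.4 | 4.3 |
| B | 2.0 | 10.2 | 7.9 | 6.6 | 4.4 | 6.2 | 3.6 |
| C | 1.2 | 6.1 | 4.8 | 4.1 | 2.6 | 3.7 | 2.1 |

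**Ratio to one test.** Under A to C it hardly depends on the direction rule. With five tests it is 4.8 to 4.9 at correlation 0, 3.2 to 3.3 at 0.7 and 2.2 to 2.3 at 0.9. With three tests it runs from about 2.9 down to 1.8. The undirected rule gives 22.7 / 5.0 = 4.5 down to 10.6 / 5.0 = 2.1 with five tests.

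**Sensitivity.**

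- Uneven correlations (0.8 among dexterity tests, 0.6 between the sensory tests, 0.3 across): A 8.9%, B 7.3%, C 4.4%. For A that is 8.9 / 2.5 = 3.6 times the one-test rate.
- Visit correlation 0.5 or 0.9 instead of 0.7, rule A: 11.9 to 12.1% at between-test correlation 0, and 5.3 to 5.7% at 0.9.
- Benefit required at both visits: 2.0% down to 1.0%, against 0.4% for one test.

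**The case against.** The strongest objection is that the inflation is conditional. The Analysis paragraph can be read as drawing one conclusion per score, with no overall claim; and if every test had to succeed there would be no inflation. That is right, and the ratio should always be quoted with its condition. It does not remove the defect, because the plan never chooses between these rules.

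Next, the efficacy family may be only the three dexterity tests. Expected Outcomes points that way, and section D describes a dexterity-focused therapy and predicts a motor gain. The ratio is then about 1.8 to 2.9. Against this, section E counts sensation as clinical hand function and the analysis covers every such score. The documents support both readings, so both ranges are given.

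The top of the range needs uncorrelated tests, which is unlikely for dexterity tests on the same hand. The uneven pattern, at about 3.6 times, may be more realistic, although the documents give no correlation. Absolute rates under the stricter direction rules are also small: under rule C they are 4.1% or less from correlation 0.7 upwards. But those rules are not in the plan. Its own undirected wording gives 10.6 to 22.7%.

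Finally, section A calls this a pilot: "The objective of this pilot project is to assess the impact of the novel sensory vibration stimulation technique". Exploratory testing would be acceptable at this size. But the plan does not describe the tests as exploratory. It ties support for the hypothesis to significance, and Expected Outcomes treats a positive result as a first demonstration of benefit.

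**Conclusion.** The concern holds. The missing primary test and missing success rule are facts of the text and rest on no assumption. The size is conditional: if any one of five tests suffices, at alpha 0.05 and between-test correlations of 0 to 0.9, a false claim of benefit is about 2 to 5 times as likely as with one named test. In absolute terms that is about 5 to 12% under rule A and 3 to 10% under B or C. The five-test ratio falls below 2 only at correlations above about 0.9. Because the list is open, five is a minimum. This should be fixed, but pilot status keeps it short of a fundamental flaw.

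**What to change.** Amend the Analysis paragraph to state alpha, name one primary hand test with one matching statistical test, and tie support to it. For example:

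> The primary outcome is [one named hand test]. The primary test is the time by group interaction at alpha 0.05, with direction read from the group difference in change from pre, averaged over post and follow-up. The hypothesis is supported if this interaction is significant and favours the experimental group. All other hand tests are exploratory.

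The group difference in change from pre to one named visit would serve equally well as the primary test. It is simpler, because it carries its own direction. The preliminary results for the Nine-Hole Peg and Box and Block tests (section C) are immediate effects with the stimulation on, so they suggest a primary but do not settle it.

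The other hand tests may instead be secondary, with Holm adjustment.

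If no single primary is chosen, close the list, apply Holm across the five named tests (smallest p below 0.05 / 5 = 0.01) and require the effect to favour the experimental group. In the simulation this holds false claims of benefit under rule A at 2.4% at correlation 0, falling to 1.2% at 0.9, and lower under B or C.

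**Cost.** Wording only, with no new data or patients. A single named primary keeps its full alpha of 0.05. Holm across five is dearer at 15 per arm: power per test at the 0.01 step falls from 59% to 34% for an assumed group difference of 0.8 SD of the change score, and from 79% to 57% for 1.0 SD (same effect at both later visits). That favours the single primary.

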Stroke survivors suffer from persistent hand impairment that diminishes their functional abilities and independence, despite multiple courses of rehabilitation. Sensory stimulation can prime central excitability to increase therapy outcome. Unlike existing methods including transcutaneous electrical nerve stimulation, muscle/tendon vibration, and repetitive transcranial magnetic stimulation (TMS) that require prior exposure to the sensory stimulation as long as 2 hours before each therapy session, we developed a new sensory stimulation technique that has the potential to immediately prime the central sensorimotor system for the hand, using imperceptible vibration applied to the wrist skin. Wearable devices with a vibrating function are low cost and can be easily adopted for rehabilitation purposes to impact a wide range of patients with sensorimotor impairment. In addition, this subthreshold vibrotactile stimulation is unique compared to the traditional stochastic resonance, by stimulating the wrist while improving fingertip tactile sensation. This remote approach exposes the entire hand to receive relevant sensory information and improve the ability to successfully manipulate objects. Despite the potential for clinical benefits and easy adoption for high impact, knowledge about the long-term efficacy of this new sensory stimulation technique and its underlying mechanism is limited. This limitation presents an obstruction to clinical adoption and optimization for efficacy.

C. PRELIMINARY STUDIES

The PI's preliminary studies showed that hand motor scores immediately improved with remote subthreshold (unperceivable) vibrotactile stimulation. Stroke survivors completed the Nine-Hole Peg and Box and Block tests faster with subthreshold (60% of the sensory threshold) vibrotactile stimulation applied to the wrist ($p < .05$) ([name] et al. 2014). The stimulation was generated by Tactor (EAI, Casselberry, FL) placed on the skin using tape. Learning effects were controlled by practice and pseudo-randomizing the stimulation off and on. Improvement in hand motor function with the stimulation was seen not only in stroke survivors but also in healthy adults (Hur et al. 2014).

Preliminary studies also showed that tactile sensation improved with the stimulation. Instantaneously with the stimulation, stroke survivors could detect smaller Semmes-Weinstein monofilaments on the fingertips, indicating improved touch sensation ($p < .01$) (Enders et al. 2013).

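### The written rule for a directional hypothesis is an unsigned 2-df interaction with no named visit or contrast; baseline enters only by subtraction and the strata are unused

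*Combined protocol and SAP*

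**What the plan says.** Section A states a directional hypothesis: "improvement in hand function will be greater for the experimental group receiving the wrist subthreshold vibrotactile stimulation during therapy compared with the control group". In Section D, the Analysis paragraph opens with a directional purpose: "Repeated measures ANOVA with post hoc comparisons will be used to determine if each clinical hand function score improves more for the experimental" group than for control. The decision sentence follows: "A significant interaction between time (pre, post, 2 weeks after) and group (experimental/control) will support the hypothesis". Expected Outcomes repeats the direction: "Greater recovery of dexterous hand function is expected with the light vibration stimulation".

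The visits are fixed earlier in Section D: "Evaluation will be performed before (pre-intervention testing), after (post-intervention testing), and 2 weeks after the therapy (follow up testing"). The same section says that "stroke subjects will be stratified by their initial hand motor and sensory scores (Fugl-Meyer and Semmes-Weinstein mild vs. moderate"), but the Analysis paragraph names no stratum term and no baseline covariate. The pre score appears only as one level of the time factor.

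Section C shows that a lower value can be the better one. On motor tests, "Stroke survivors completed the Nine-Hole Peg and Box and Block tests faster with subthreshold" stimulation. On sensation, "stroke survivors could detect smaller Semmes-Weinstein monofilaments on the fingertips, indicating improved touch sensation".

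**The concern.** The hypothesis says which group should improve more. The decision sentence asks only whether the two groups' time profiles differ. An F test on 2 df can be significant because vibration did better, because control did better, or because the groups differed in opposite directions at post and at follow-up. Post hoc comparisons could settle which, but the plan does not say at which visit they are made, against which contrast, or that support depends on them. The favourable sign for each score is not listed either.

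What is at stake is the choice left open after the data are seen. If the two visits disagree, the analyst has to decide which one counts, and that decision can determine the conclusion. A secondary matter is efficiency: baseline and the stratification factors are already collected, and the planned test makes less use of them than it could.

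**Working it through.** **Inputs.** From the documents: three visits and two groups (Section D), 15 per group (Section E.1.a). There is no power figure to reproduce. Assumed: SD 1, equal correlation r between visits, two-sided 5%, no dropout, and a 0.5 SD effect where not stated otherwise.

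**Degrees of freedom.** Interaction (3−1)(2−1) = 2; error (3−1)(30−2) = 56.

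**Interaction power.** Noncentral F(2,56) with λ = (15/2) × Σ(g − mean g)² / (1−r), where g is the group difference at pre, post and follow-up.
- Constant benefit, g = (0, 0.5, 0.5): the sum of squares is 1/9 + 1/36 + 1/36 = 1/6, so λ = 1.25/(1−r).
- Constant harm, g = (0, −0.5, −0.5): same sum, so the same λ and the same power.
- Mixed, g = (0, 0.5, −0.5): the mean is 0 and the sum is 0.5, so λ = 3.75/(1−r).

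**How often the rule is met when vibration is not better on average.** The sign and both-visit rows come from 40,000 simulated trials per scenario.

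| | r=0.5 | 0.6 | 0.7 | 0.8 |
|---|---|---|---|---|
| Harm, rule read literally | 26% | 32% | 41% | 58% |
| Harm, plus mean change favours vibration | 0.12% | 0.06% | 0.04% | 0.00% |
| Mixed, rule read literally | 66% | 76% | 88% | 97% |
| Mixed, plus mean change favours vibration | 33% | 38% | 44% | 49% |
| Mixed, plus change favours vibration at both visits | 4.0% | 3.6% | 2.8% | 1.4% |

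An averaged, baseline-adjusted contrast declares support in about 2.5% of mixed-pattern trials, the favourable half of a two-sided 5% test. A sign clause alone therefore cures the harm case but not the mixed case.

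**Use of baseline.** The interaction subtracts baseline in full. With no treatment effect and an observed baseline gap of b, the expected difference in change is rb − b = −(1−r)b. At r = 0.6 and b = 0.5 SD this is −0.2 SD, so the gap is over-corrected. Over all randomisations the type I error is still about 5%.

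**Efficiency for a constant 0.5 SD benefit.** The formulas, with r = 0.6 worked through:
- Averaged change: residual variance 1.5(1−r) = 0.60; SE = √(0.60 × 2/15) = 0.283; 0.5/0.283 = 1.77 on 28 df.
- Averaged, baseline as covariate: variance (1+r)/2 − r² = 0.44; SE = √(0.44 × (2/15)(1+1/27)) = 0.247; 0.5/0.247 = 2.03 on 27 df.
- Post only, baseline as covariate: variance 1−r² = 0.64; SE = √(0.64 × (2/15)(1+1/27)) = 0.297; 0.5/0.297 = 1.68 on 27 df.

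| Power | r=0.5 | 0.6 | 0.7 | 0.8 | 0.9 |
|---|---|---|---|---|---|
| Planned interaction | 26% | 32% | 41% | 58% | 88% |
| Averaged change | 33% | 40% | 50% | 68% | 93% |
| Averaged, adjusted | 45% | 50% | 58% | 72% | 93% |
| Post only, adjusted | 32% | 37% | 44% | 58% | 84% |

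At r = 0.6 the gain over the interaction is 50 − 32 = 18 points: 8 from naming a 1-df contrast and 10 from adjustment. At r = 0.9 adjustment adds under 1 point over averaged change (93.4% v 92.7%).

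**Other time patterns, r = 0.6.**

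| Effect at post, follow-up (SD) | Interaction | Post only, adjusted | Averaged, adjusted |
|---|---|---|---|
| 0.8, 0.4 | 56% | 74% | 65% |
| 0.4, 0.8 | 56% | 25% | 65% |
| 0.8, 0 | 69% | 74% | 35% |

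**The case against.** The strongest reply is that the decision sentence should not be read in isolation. The hypothesis, the purpose sentence and Expected Outcomes all give the direction. So does the passage in Section D on why two weeks of therapy is thought sufficient. A reader might infer from the 26–58% figures that the plan would credit vibration when it did worse. The documents do not support that: an interaction favouring control could not reasonably be reported as support. If one change-score post hoc comparison had to be significant and favour vibration, support in the harm case would fall to 0.05% or less at every r from 0.5 to 0.8. This stands, and it makes the sign clause a clarification. It does not close the visit gap. If a favourable post hoc result at either visit sufficed, the mixed pattern would still give support in 25–55% of trials.

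A reader might also infer that the ANOVA is invalid or ignores baseline. Neither is so. Its overall error rate is about 5%, and it removes baseline by subtraction. Stratification on initial motor and sensory scores also limits imbalance.

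Two further replies have weight. The mixed pattern is a stress case, and nothing in the documents predicts it. And an omnibus test is defensible in a pilot whose time course is unknown: it beats the averaged contrast when an effect is gone by follow-up, and beats the post-only contrast when r is 0.9. Baseline adjustment is therefore an efficiency recommendation, and its value depends on a correlation that the documents do not give.

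**Conclusion.** The point holds and should be fixed. The only written decision rule has no sign and names no visit or contrast, and nothing makes support conditional on the post hoc comparisons. Since the direction is clear from context, the part that matters most is the unnamed contrast: it leaves 33–49% support for a zero-average mixed pattern even after a sign check. The efficiency part is real but secondary: 14 to 19 points over the interaction at r = 0.5 to 0.8 for a sustained 0.5 SD benefit, and about 5 points at r = 0.9, almost all of the latter from averaging. All sizes rest on assumed effects, equal correlation, 15 complete participants per arm and a two-sided 5% test. That the rule is unsigned and tied to no visit follows from the text alone.

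**What to change.** 1. Amend the Analysis paragraph so that the hypothesis is supported for a score only if a contrast named before unblinding is significant and favours vibration. The contrast may be the average of post and follow-up, or one named visit. State the favourable sign for each score. Shorter Nine-Hole Peg time and a smaller detectable monofilament follow from Section C. The sponsor should state the others, including whether Box and Block is scored as a time.
2. Estimate the contrast with the baseline score as covariate and the Fugl-Meyer and Semmes-Weinstein strata as factors. When Semmes-Weinstein is itself the outcome, keep only one of its baseline score and its mild/moderate stratum, because the two largely duplicate each other.
3. If the ANOVA is kept, the minimum change is the sign clause plus the visit or visits at which the change must favour vibration. Requiring both visits keeps 25/31/41/57% power at r = 0.5/0.6/0.7/0.8 for a constant 0.5 SD benefit.

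The cost is wording, with no new data. The sign clause changes power for a sustained benefit by 0.1 point or less. The two stratum terms take 2 of 27 residual df; in simulation with strata weakly related to the score (latent correlation 0.3) they moved power by about a point either way. The real cost is lost sensitivity off target. At r = 0.6, for a 0.8 SD effect gone by follow-up, power falls from 69% to 35% with the averaged contrast, and likewise if both visits must be favourable. For an effect growing from 0.4 to 0.8 SD, a post-only contrast has 25% against 56%. The choice of contrast is therefore the sponsor's. Multiplicity across the several scores is a separate matter that this change does not settle.
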